Appendix 1 Schedule of Activities (cont.)

- ⁱ Hematology includes WBC count, RBC count, hemoglobin, hematocrit, platelet count, reticulocyte count, differential count (neutrophils, eosinophils, basophils, monocytes, and lymphocytes).
- ^j Includes anti-nuclear antibody, anti-double-stranded DNA, circulating anti-neutrophil cytoplasmic antibody, and perinuclear anti-neutrophil cytoplasmic antibody.
- ^k Chemistry panel (serum or plasma) includes sodium, potassium, chloride, bicarbonate (or total carbon dioxide), BUN or urea, creatinine, total protein, magnesium, phosphorus, calcium, total and direct bilirubin, ALP, ALT, AST, CPK, LDH, uric acid; albumin, non-fasting glucose (fasting blood glucose after a minimum 8-hour fast, at screening only), lipids, (Fasting lipids: total cholesterol, LDL cholesterol, and triglycerides after a minimum 8-hour fast, at screening only).
- ^l Tumor assessments will continue until disease progression per RECIST v1.1, loss of clinical benefit (patients who continue treatment after disease progression according to RECIST v1.1), consent withdrawal, study termination by the Sponsor, or death, whichever occurs first. At the investigator's discretion, tumor assessments may be repeated at any time if disease progression is suspected. Patients who discontinue treatment for reasons other than disease progression (e.g., toxicity) will continue scheduled tumor assessments until disease progression, withdrawal of consent, study termination by Sponsor, or death, whichever occurs first.
- ^m All patients will undergo evaluation of left ventricular dysfunction, either by ECHO or MUGA scan, at screening. Evaluation of LVEF by ECHO or MUGA scan must be performed at the following time points only for patients taking cobimetinib:
- Cycle 2, Day 1 (± 1 week)
 - Day 1 of Cycles 5, 8, 11, 14, 17, etc. (every three treatment cycles) ± 2 weeks
 - Treatment discontinuation visit evaluation of LVEF does not need to be performed at treatment discontinuation visit if an evaluation has been performed within the last 12 weeks and there are no clinically significant findings and/or changes from baseline.
 - All patients restarting treatment with a dose reduction of cobimetinib because of a decrease in LVEF should have LVEF measurements taken after approximately 2, 4, 10, and 16 weeks, and then resume monitoring LVEF every three treatment cycles.
- ⁿ All patients will be tested for HIV prior to the inclusion into the study and HIV-positive patients will be excluded from the clinical study.
- HBV serology will include HBsAg, total HBcAg antibody (anti-HBcAb). HBV DNA should be obtained prior to study start if patient has a negative serology for HBsAg and a positive serology for anti-HBcAb.
 - HCV serology will include HCV antibody (anti-HCV). HCV RNA should be obtained prior to study start if patient tests positive for anti-HCV.
- ^o Thyroid function testing (TSH, free T3 [or total T3 for sites where free T3 is not performed, free T4] collected at Day 1 of Cycles 1–5, and every second cycle thereafter (e.g., Day 1 of Cycles 7, 9, 11, etc.) for patients on atezolizumab only.
- ^p All women of childbearing potential will have a serum pregnancy test at screening within 14 days prior to Day 1 of Cycle 1. Urine pregnancy tests will be performed on Day 1 of every cycle and at the treatment discontinuation visit. If a urine pregnancy test is positive, it must be confirmed by a serum pregnancy test.

Appendix 1

Schedule of Activities (cont.)

- ^q Includes dipstick (pH, specific gravity, glucose, protein, ketones, blood) and microscopic examination (sediment, RBCs, WBCs, casts, crystals, epithelial cells, bacteria).
- ^r Includes any medication (e.g., prescription drugs, over-the-counter drugs, herbal or homeopathic remedies, nutritional supplements) used by a patient from 7 days before initiation of study drug until 30 days after the last dose of study drug.
- ^s After informed consent has been obtained but prior to initiation of study drug, only serious adverse events caused by a protocol-mandated intervention should be reported. After initiation of study drug, all adverse events will be reported until 90 days after the last dose of study drug or initiation of new anti-cancer therapy, whichever occurs first. After this period, all deaths, regardless of cause, should be reported. After this period, the Sponsor should be notified if the investigator becomes aware of any serious adverse event that is believed to be related to prior study drug treatment (see Section 5.6). The investigator should follow each adverse event until the event has resolved to baseline grade or better, the event is assessed as stable by the investigator, the patient is lost to follow-up, or the patient withdraws consent. Every effort should be made to follow all serious adverse events or adverse events of special interest considered to be related to study drug or trial-related procedures until a final outcome can be reported.
- ^t Archival (< 5 years old) or fresh baseline tumor tissue collected during screening. If a patient provides a fresh biopsy for *BRAF*^{V600} testing, this sample will be used also as baseline for biomarker analysis. Therefore predose specimens are not required for patients who provide a fresh biopsy before treatment start. If archival tissue is used availability of adequate tumor tissue must be confirmed prior to any screening procedures (paraffin-embedded tumor block or a minimum of 20 unstained slides). Submit archival tissue and associated pathology report within 30 days after Cycle 1, Day 1. If a predose fresh biopsy is collected this sample should be obtained after eligibility criteria have been fulfilled and prior to Cycle 1, Day 1. For patients who have consented to optional biopsies a subsequent biopsy may be performed 4-6 weeks after the first atezolizumab administration; an additional optional biopsy may be collected at the time of radiographic progression if clinically feasible. See Section 3.1.1 and the laboratory manual for further details.
- ^u In Cohort A, atezolizumab will be given on Days 1 and 15 of all cycles. The initial dose will be delivered over 60 (\pm 15) minutes. If the first infusion is well tolerated, all subsequent infusions will be delivered over 30 (\pm 10) minutes until loss of clinical benefit. Study drug administration may be \pm 3 days from the scheduled Day 1 and 15 of each cycle.
- ^v Cobimetinib 60 mg/day by mouth will be given in a 21/7 dosing schedule.

Appendix 1
Schedule of Activities (cont.)
Cohort B: Biopsy Cohort

	Screening ^a	Cycle 1		Cycle 2		Cycle 3+		Treatment Discontinuation ^b	Unplanned Visit ^c	Survival FU ^d
Day (window)	-35 to -1	1	15	1	15	1	15	30 (±3) days after last dose		Q3M
Informed consent ^e	x									
Demographic data	x									
Medical history	x									
Vital signs ^{f,g}	x	x	x	x	x	x	x	x	x	
ECOG PS	x	x		x		x			x	
Weight	x	x		x		x		x		
Height	x									
Complete physical examination	x							x		
Limited physical examination		x ^h		x		x				
Hematology ⁱ	x	x		x		x		x	x	
Coagulation (INR and aPTT)	x									
BRAF ^{V600} WT mutation status	x									
PK and ADA sample for atezolizumab	See Appendix 2								x	x
PK sample for cobimetinib	See Appendix 2									
Serum samples for auto-antibody tests ^j		x								

Appendix 1
Schedule of Activities (cont.)
Cohort B: Biopsy Cohort

	Screening ^a	Cycle 1		Cycle 2		Cycle 3+		Treatment Discontinuation ^b	Unplanned Visit ^c	Survival FU ^d
Day (window)	-35 to -1	1	15	1	15	1	15	<30 (±3) days after last dose		Q3M
Optional WGS		x								
Chemistry ^k	x	x		x		x		x	x	
Tumor assessments ^l	x	Scans will be done every 8 weeks ± 7 days								
ECHO/MUGA scan	x			x		x ^m		x	x	
ECG (average of triplicate measurements)	x								x	
Serology ⁿ	x									
Thyroid function ^o	x	x		x		x ^o		x		
Ophthalmologic exam	x	Perform ophthalmology investigations as per Section 4.4.7.								
Pregnancy test ^p	x	x		x		x ^p		x	x	
Urinalysis ^q	x									
Concomitant medications ^r	x ^r	x ^r		x		x		x ^r		
Adverse events ^s	x ^s	x ^s	x	x	x	x	x	x ^s		x ^s
Tumor biopsy ^t	x		x ^u	x				x		
Biomarker blood samples		See Appendix 2								
Atezolizumab administration ^v			x	x	x	x	x			
Dispense cobimetinib ^w		x		x		x				
Survival and anti-cancer therapy FU										x

Appendix 1

Schedule of Activities (cont.)

ADA=anti-drug antibody; CPK=increased creatine phosphokinase; ECHO=echocardiogram; ECOG PS=Eastern Cooperative Oncology Group performance status; eCRF=electronic Case Report Form; FU=follow-up; HBcAb=hepatitis B core antibody; HBcAg=hepatitis B core antigen; HBsAg=hepatitis B surface antigen; HBV=hepatitis B virus; HCV=hepatitis C virus; LVEF=left ventricular ejection fraction; MUGA=multiple-gated acquisition; PD=progressive disease; PK=pharmacokinetic; Q3M=every 3 months; RECIST=Response Evaluation Criteria in Solid Tumors; T3=triiodothyronine; T4=thyroxine; TSH=thyroid-stimulating hormone; WGS=whole genome sequencing; WT=wild type.

Notes: All assessments should be performed within ± 3 days of the scheduled visit, unless otherwise specified. On treatment days, all assessments should be performed prior to dosing, unless otherwise specified. On treatment days, pre-infusion laboratory samples should be drawn up to 4 hours before the start of infusion, and post-infusion laboratory samples should be drawn up to 30 minutes after the end of infusion, unless otherwise specified.

- ^a Results of standard-of-care tests or examinations performed before obtaining informed consent and within 35 days before Day 1 may be used; such tests do not need to be repeated for screening. *BRAF*^{V600} status must be known prior to performing study-specific screening assessments. The 35-day window begins at the time of the first standard-of-care screening assessment or the first study-specific screening assessment after the *BRAF*^{V600} mutation test result is available, whichever is earlier. Test results should be reviewed before study treatment is given.
- ^b Patients who discontinue study drug will return to the clinic for a treatment discontinuation visit at 30 (± 3) days. The visit at which response assessment shows PD may be used as the study discontinuation visit.
- ^c Visit not specified by the protocol. Assessments (possibly including PK sample collection) should be performed as clinically indicated.
- ^d Required follow-up information will be collected via telephone calls and/or clinic visits every 3 months until death, loss to follow-up, or study termination by the Sponsor.
- ^e Informed consent must be documented before any study-specific screening procedure is performed and may be obtained up to 35 days before initiation of study treatment.
- ^f Includes respiratory rate, heart rate, and systolic and diastolic blood pressure (monitored after the patient has been in a seated position for 5 min), and temperature (oral or tympanic). Resting oxygen saturation may be measured at screening. Record abnormalities observed at baseline on the General Medical History and Baseline Conditions eCRF. At subsequent visits, record new or worsened clinically significant abnormalities on the Adverse Event eCRF.
- ^g Vital signs at the first atezolizumab infusion will be collected within 60 minutes before the infusion, every 15 (± 5) min during the atezolizumab infusion, and 30 (± 10) min after the infusion. For subsequent infusions, vital signs will be collected within 60 min before the infusion and during the infusion (if clinically indicated or if symptoms occurred in the prior infusion), and 30 (± 10) min after the infusion.

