5.2.3 Adverse Events of Special Interest (Immediately Reportable to the Sponsor)

Adverse events of special interest are required to be reported by the investigator to the Sponsor immediately (i.e., no more than 24 hours after learning of the event; see Section 5.4.2 for reporting instructions). Adverse events of special interest for this study include the following:

- Significant liver toxicity
- Cases of potential drug-induced liver injury that include an elevated ALT or AST in combination with either an elevated bilirubin or clinical jaundice, as defined by Hy's Law (see Section 5.3.5.7) and based on the following observations:
 - Treatment-emergent ALT or AST $> 3 \times$ baseline value in combination with total bilirubin $> 2 \times$ ULN (of which $\geq 35\%$ is direct bilirubin)
 - Treatment-emergent ALT or AST $> 3 \times$ baseline value in combination with clinical jaundice
 - Hepatitis, including AST or ALT $> 10 \times$ ULN
- Suspected transmission of an infectious agent by the study drug, as defined below
 - Any organism, virus, or infectious particle (e.g., prion protein–transmitting transmissible spongiform encephalopathy), pathogenic or non-pathogenic, is considered an infectious agent. A transmission of an infectious agent may be suspected from clinical symptoms or laboratory findings that indicate an infection in a patient exposed to a medicinal product. This term applies only when a contamination of the study drug is suspected.
- Pneumonitis
- Colitis
- Endocrinopathies: diabetes mellitus, pancreatitis, adrenal insufficiency, hyperthyroidism, and hypophysitis
- Systemic lupus erythematosus
- Neurologic disorders: Guillain-Barré syndrome, myasthenic syndrome or myasthenia gravis, and meningoencephalitis
- Nephritis
- Events suggestive of hypersensitivity, infusion-related reactions, cytokine-release syndrome, influenza-like illness, systemic inflammatory response system
- Ocular toxicities
 - Uveitis
 - RVO
 - Serous retinopathy
 - Myositis

- Cardiac disorders for the following events:
 - Grade ≥ 2 cardiac disorders, including atrial fibrillation, myocarditis, and pericarditis
 - Symptomatic heart failure or Grade ≥ 3 reduction in LVEF
- Vasculitis
- Myopathies, including rhabdomyolysis or Grade ≥ 3 CPK elevation
- Grade ≥ 3 hemorrhage or any-grade cerebral hemorrhage
- Grade ≥ 3 rash
- Grade ≥ 3 diarrhea

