5.3.1 Adverse Event Reporting Period

Investigators will seek information on adverse events at each patient contact. All adverse events, whether reported by the patient or noted by study personnel, will be recorded in the patient's medical record and on the Adverse Event eCRF.

After informed consent has been obtained **but prior to initiation of study drug**, only serious adverse events caused by a protocol-mandated intervention (e.g., invasive procedures such as biopsies, discontinuation of medications) should be reported (see Section 5.4.2 for instructions for reporting serious adverse events).

After initiation of study drug, all adverse events will be reported until 90 days after the last dose of study drug. After this period, the investigator should report any serious adverse events that are believed to be related to prior study drug treatment (see Section 5.6).

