5.4.2.2 Events That Occur after Study Drug Initiation

After initiation of study drug, serious adverse events and adverse events of special interest will be reported until 90 days after the last dose of study drug. Investigators should record all case details that can be gathered immediately (i.e., within 24 hours after learning of the event) on the Adverse Event eCRF and submit the report via the electronic data capture (EDC) system. A report will be generated and sent to Roche Safety Risk Management by the EDC system.

In the event that the EDC system is unavailable, the Serious Adverse Event/Adverse Event of Special Interest Reporting Form provided to investigators should be completed and submitted to the Sponsor or its designee immediately (i.e., no more than 24 hours after learning of the event), either by faxing or by scanning and emailing the form using the fax number or email address provided to investigators. Once the EDC system is available, all information will need to be entered and submitted via the EDC system.

Instructions for reporting serious adverse events that occur >90 days after the last dose of study treatment are provided in Section 5.6.

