5.6 ADVERSE EVENTS THAT OCCUR AFTER THE ADVERSE EVENT REPORTING PERIOD

After the end of the adverse event reporting period (defined as 90 days after the last dose of study drug), all deaths, regardless of cause, should be reported through use of the Long-Term Survival Follow-Up eCRF. In addition, if the investigator becomes aware of a serious adverse event that is believed to be related to prior study drug treatment, the event should be reported through use of the Adverse Event eCRF.

5.7 EXPEDITED REPORTING TO HEALTH AUTHORITIES, INVESTIGATORS, INSTITUTIONAL REVIEW BOARDS, AND ETHICS COMMITTEES

The Sponsor will promptly evaluate all serious adverse events and adverse events of special interest against cumulative product experience to identify and expeditiously communicate possible new safety findings to investigators, IRBs, ECs, and applicable health authorities based on applicable legislation.

To determine reporting requirements for single adverse event cases, the Sponsor will assess the expectedness of these events using the following reference documents:

- Cobimetinib Investigator's Brochure
- Atezolizumab Investigator's Brochure

The Sponsor will compare the severity of each event and the cumulative event frequency reported for the study with the severity and frequency reported in the applicable reference document.

Reporting requirements will also be based on the investigator's assessment of causality and seriousness, with allowance for upgrading by the Sponsor as needed.

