Appendix 7 Anaphylaxis Precautions

PRECAUTIONS

Equipment needed:

- Tourniquet
- Oxygen
- Epinephrine for subcutaneous, intravenous (IV), and/or endotracheal use in accordance with standard practice
- Antihistamines
- Corticosteroids
- IV infusion solutions, tubing, catheters, tape

PROCEDURES

In the event of a suspected anaphylactic reaction during study drug infusion, the following procedures should be performed:

1. Stop the drug infusion.
2. Apply a tourniquet proximal to the injection site to slow systemic absorption of study drug. Do not obstruct arterial flow in the limb.
3. Maintain adequate airway.
4. Administer antihistamines, epinephrine, or other medications as required by patient status and directed by physician in charge.
5. Continue to observe the patient and document observations

Appendix 8

Risks Associated with Atezolizumab and Guidelines for Management of Adverse Events Associated with Atezolizumab

Toxicities associated or possibly associated with atezolizumab treatment should be managed according to standard medical practice. Additional tests, such as autoimmune serology or biopsies, should be used to evaluate for a possible immunogenic etiology.

Although most immune-related adverse events observed with immunomodulatory agents have been mild and self-limiting, such events should be recognized early and treated promptly to avoid potential major complications. Discontinuation of atezolizumab may not have an immediate therapeutic effect, and in severe cases, immune-related toxicities may require acute management with topical corticosteroids, systemic corticosteroids, or other immunosuppressive agents.

The investigator should consider the benefit–risk balance a given patient may be experiencing prior to further administration of atezolizumab. In patients who have met the criteria for permanent discontinuation, resumption of atezolizumab may be considered if the patient is deriving benefit and has fully recovered from the immune-related event. Patients can be re-challenged with atezolizumab only after approval has been documented by both the investigator (or an appropriate delegate) and the Medical Monitor.

PULMONARY EVENTS

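### Appendix 1 ends adverse event reporting at the start of new anti-cancer therapy, whereas Sections 5.3.1, 5.4.2.2 and 5.6 run it to 90 days after the last dose; the scan-stop rules also differ

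*Combined protocol and SAP*

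**What the plan says.** **Adverse event window.** Section 5.3.1 covers all adverse events: "After initiation of study drug, all adverse events will be reported until 90 days after the last dose of study drug". Section 5.4.2.2 says the same for the expedited categories: "serious adverse events and adverse events of special interest will be reported until 90 days after the last dose of study drug". Section 5.6 fixes the term itself: "adverse event reporting period (defined as 90 days after the last dose of study drug"). Footnote s in each of the three Appendix 1 schedules instead says "all adverse events will be reported until 90 days after the last dose of study drug or initiation of new anti-cancer therapy", whichever comes first. It then adds "After this period, all deaths, regardless of cause, should be reported" and, for later serious events, that the Sponsor "should be notified if the investigator becomes aware of any serious adverse event that is believed to be related" to earlier study drug. Section 5.2.3 is unconditional on events of special interest: "Adverse events of special interest are required to be reported by the investigator to the Sponsor immediately". Section 6.5 summarizes adverse events from the first dose onward and names no end date.

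**Tumor assessments.** Section 3.1 ends them at progression, death or subsequent anti-cancer therapy. Section 4.4.5 ends them at confirmed progression or death. Footnote l, in all three schedules, lists progression, loss of clinical benefit, withdrawal of consent, study termination and death. Neither of the last two mentions new therapy. Section 6.4.1 defines ORR and DCR without reference to new therapy.

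**The concern.** Section 4.4 sends sites to Appendix 1 for the activities to be performed, so a site could follow footnote s in good faith and stop recording earlier than Section 5 requires. The conflict applies to any patient who starts another cancer treatment within 90 days of the last dose, including after progression. It is therefore not limited to unusual cases.

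Events never collected cannot be restored at analysis. Events collected after a switch can be flagged and shown separately. If some sites use one rule and some the other, the Section 6.5 summaries cover different lengths of observation for different patients, and nothing in that section shows the difference.

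The scan conflict raises a narrower question. Where a site keeps scanning under Section 4.4.5 or footnote l, a response or stable disease recorded on another drug could be credited to study treatment, because Section 6.4.1 does not exclude it.

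**Working it through.** **1. The two windows.** Count days from the last dose and let d be the day new therapy starts, with d below 90.

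- Section 5.3.1: reporting ends at day 90.
- Footnote s: reporting ends at min(90, d) = d.
- Difference: 90 − d days.

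The documents give no distribution for d. For assumed values:

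- d = 14: 90 − 14 = 76 days
- d = 28: 90 − 28 = 62 days
- d = 42: 90 − 42 = 48 days
- d = 60: 90 − 60 = 30 days

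**2. What falls in the gap.** Sorting events between day d and day 90 by the text of footnote s:

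- Deaths from any cause: still reported.
- Serious events believed related: still reported if the investigator becomes aware of them.
- Events already present at the switch: still followed, because footnote s and Section 5.5.1 both require follow-up to resolution or stability. Section 5.3.5.4 records worsening.
- New-onset serious events not believed related: not reported.
- New-onset non-serious events: not reported. This includes non-serious events of special interest, although Sections 5.2.3 and 5.4.2.2 require them.

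**3. Can the loss be counted?** It would be (patients who switch before day 90) × (mean of 90 − d) × (rate of such events per day). None of the three factors is in the documents. Scheduled chances to detect these events are also limited. Appendix 1 marks adverse events at the 30 (±3)-day visit and at three-monthly follow-up. Appendix 2 adds a sample visit at 120 (±30) days, so no earlier than 120 − 30 = day 90. Section 5.3.1 asks for adverse events at each patient contact.

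**4. ORR and DCR.** The protocol's example for Cohorts A and B is 26 responders of 102. The Clopper-Pearson limits are the 0.025 quantile of Beta(x, n − x + 1) and the 0.975 quantile of Beta(x + 1, n − x). With x = 26 and n = 102 these give 25.49% (17.38, 35.08), matching the printed 25.5% (17.4%, 35.1%). If one patient is reclassified:

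- Cohorts A and B: 1/102 = 0.98 points. ORR 26/102 = 25.5% becomes 25/102 = 24.5%. DCR 60/102 = 58.8% becomes 59/102 = 57.8%.
- Cohort C: 1/50 = 2.0 points. ORR 17/50 = 34.0% becomes 16/50 = 32.0%. DCR 32/50 = 64.0% becomes 31/50 = 62.0%.

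These are per-patient effects. The number of such patients is not given.

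**The case against.** The best defense is that the footnote is plainly the outlier. Three body sections agree, and footnote s itself points to Section 5.6, which defines the period as 90 days. A careful site or monitor would settle on the longer window. This makes the loss conditional on how sites read the text. It does not remove the contradiction, since I found no statement that the body prevails over Appendix 1. Some events after a switch will also be due to the next drug. That is true, and it is a reason to flag them.

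Three stronger readings are tempting and are not supported:

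- Appendix 8 says "Discontinuation of atezolizumab may not have an immediate therapeutic effect", from which a reader might infer that continuing immune toxicity would go unrecorded. In context the sentence is about managing toxicity already present, and such events are still followed. It says nothing about new onset after a switch.
- With 25 of 102 responders the exact lower limit is 16.5%, below the 17% historical response rate cited in Section 6.1. A reader might infer that the ORR gap could reverse that comparison. Section 6.1 plans no formal testing, and the number of affected patients is unknown. Section 4.3.2 bars other cancer therapy until progression is documented and study treatment has stopped, with exceptions for palliative radiotherapy and some local therapy.
- A reader might infer that the gap can only inflate both endpoints. For DCR that is unsettled. Under Section 3.1 a confirmed responder who switches before Week 16 would have no Week 16 scan, and the plan does not say how that patient counts.

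**Conclusion.** The contradiction is real, is in current text, and recurs in all three schedules. The adverse event window carries the point. It puts at risk new-onset non-serious events, including those of special interest, and serious events not believed related, in patients who switch within 90 days at sites that follow footnote s. Deaths, related serious events that become known, and follow-up of existing events are not at risk. The size cannot be derived, because the documents give neither the frequency or timing of switching nor the event rate after the last dose.

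The scan-stop conflict is also real but secondary. Use of other therapy before progression should be rare given Section 4.3.2, although Section 4.5.3 foresees it by listing it as a reason to stop study treatment. Each such patient would move an estimate by about 1 point in Cohorts A and B or 2 points in Cohort C, and no test depends on it. This should be corrected, but it does not undermine the design.

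**What to change.** 1. In footnote s of all three Appendix 1 tables, delete the clause that ends reporting early at new anti-cancer therapy, so that it matches Sections 5.3.1, 5.4.2.2 and 5.6. State the same window in Section 6.5 and flag events with onset after new therapy.
2. Reconcile the scan-stop rule across Section 3.1, Section 4.4.5 and footnote l.
3. Add to Section 6.4.1 that a response or disease control first recorded after the start of new anti-cancer therapy does not count toward ORR or DCR. State how a confirmed responder who switches before Week 16 is counted for DCR.

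The cost is a protocol amendment under Section 9.6, with ethics and, where locally required, regulatory approval across about 60 centers. There will also be a few more adverse event reports after switching, some attributable to the next drug. Section 4.5.3 already collects subsequent anti-cancer therapy. The sponsor should check that the start date is recorded, since both the flag and the Section 6.4.1 rule need it.
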